10.8. Appendix 8: Case Definitions for COVID-19

10.8.1. Adults Case Definition for Moderate to Severe/Critical COVID-19

Case Definition for Moderate COVID-19

- A SARS-CoV-2 positive RT-PCR or molecular test result from any available respiratory tract sample (eg, nasal swab sample, sputum sample, throat swab sample, saliva sample) or other sample.

AND at any time during the course of observation^a:

Any 1 of the following new or worsening signs or symptoms:

- Respiratory rate ≥ 20 breaths/minute
- Abnormal saturation of oxygen (SpO_2) but still $>93\%$ on room air at sea level*
- Clinical or radiologic evidence of pneumonia
- Radiologic evidence of DVT
- Shortness of breath or difficulty breathing

OR

Any 2 of the following new or worsening signs or symptoms:

- Fever ($\geq 38.0^\circ C$ or $\geq 100.4^\circ F$)
- Heart rate ≥ 90 beats/minute
- Shaking chills or rigors
- Sore throat
- Cough
- Malaise as evidenced by 1 or more of the following^{**}:
 - Loss of appetite
 - Generally unwell
 - Fatigue
 - Physical weakness
- Headache
- Muscle pain (myalgia)
- Gastrointestinal symptoms (diarrhea, vomiting, nausea, abdominal pain)
- New or changing olfactory or taste disorders
- Red or bruised looking feet or toes

SpO_2 criteria will be adjusted according to altitude.

^{**} Having 2 or more elements of a symptom (eg, vomiting and diarrhea or fatigue and loss of appetite) is counted only as 1 symptom for the case definition. To meet the case definition, a participant would need to have at least 2 different symptoms.

^a Participants will be asked to undertake the COVID-19 procedures until 14 days after symptom onset (COVID-19 Day 15) or until **resolution of the COVID-19 episode**, whichever comes last (see Section 8.1.2).

Case Definition for Severe/Critical COVID-19

- A SARS-CoV-2 positive RT-PCR or molecular test result from any available respiratory tract sample (eg, nasal swab sample, sputum sample, throat swab sample, saliva sample) or other sample

AND any 1 of the following at any time during the course of observation^a:

- Clinical signs at rest indicative of severe systemic illness (respiratory rate ≥ 30 breaths/minute, heart rate ≥ 125 beats/minute, oxygen saturation [SpO₂] $\leq 93\%$ on room air at sea level*, or partial pressure of oxygen/fraction of inspired oxygen [PaO₂/FiO₂] < 300 mm Hg)

* SpO₂ criteria will be adjusted according to altitude.

- Respiratory failure (defined as needing high-flow oxygen, non-invasive ventilation, mechanical ventilation, or extracorporeal membrane oxygenation [ECMO])
- Evidence of shock (defined as systolic blood pressure < 90 mm Hg, diastolic blood pressure < 60 mm Hg, or requiring vasopressors)
- Significant acute renal, hepatic, or neurologic dysfunction
- Admission to the ICU
- Death

10.8.2. Adult Case Definition for Mild COVID-19

- A SARS-CoV-2 positive RT-PCR or molecular test result from any available respiratory tract sample (eg, nasal swab sample, sputum sample, throat swab sample, saliva sample) or other sample;

AND at any time during the course of observation^a:

- One of the following symptoms: fever ($\geq 38.0^\circ\text{C}$ or $\geq 100.4^\circ\text{F}$), sore throat, malaise (loss of appetite, generally unwell, fatigue, physical weakness), headache, muscle pain (myalgia), gastrointestinal symptoms, cough, chest congestion, runny nose, wheezing, skin rash, eye irritation or discharge, chills, new or changing olfactory or taste disorders, red or bruised looking feet or toes, or shaking chills or rigors.

A case is considered clinically mild when it meets the above case definition but not the moderate to severe/critical definition in Section [10.8.1](#).

^a Participants will be asked to undertake the COVID-19 procedures until 14 days after symptom onset (COVID-19 Day 15) or until **resolution of the COVID-19 episode**, whichever comes last (see Section [8.1.2](#)).

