In adults, the most frequently reported solicited local AE was injection site pain (56.9% of Ad26 participants, compared with 22.5% of placebo participants). All other solicited local AEs were experienced by less than 25% of adult participants. The most frequently experienced solicited local AE in children was injection site pain, reported in 13.9% of children aged 1-3 years, 29.8% of children aged 4-11 years, and 24.8% of children aged 12-17 years after vaccination with an Ad26-based vaccine. For placebo, these percentages were 29.2% in children aged 4-11 years and 14.3% in children aged 12-17 years. No children aged 1-3 years have received placebo.

Severe injection site pain was experienced by 1.0% of adult Ad26 participants and 0.8% of children aged 4-11 years. No children in the other 2 age groups and no placebo participants experienced severe injection site pain.

There was a trend toward an increase in the frequency of some local AEs with an increase in Ad26 dose, ie, injection site pain (18.7% of participants at the 0.8×10^{10} vp dose level, 38.7% of participants at the 2×10^{10} vp dose level, 52.0% of participants at the 5×10^{10} vp dose level, and 77.1% of participants at the 1×10^{11} vp dose level), and to a lesser extent injection site swelling (6.7%, 2.7%, 9.3%, and 17.6%, respectively). Injection site warmth was not collected at the 0.8×10^{10} vp and the 2×10^{10} vp dose level. The frequency of injection site warmth at the 5×10^{10} vp and the 1×10^{11} vp dose level was 19.5%, and 26.7%, respectively. This trend needs to be interpreted with caution since the participants in the lower dose groups (0.8×10^{10} vp and 2×10^{10} vp

dose level) were all from a single study (VAC52150EBL3002), and the majority of the participants in the highest dose group (1×10^{11} vp dose level) were also from a single study (VAC18193RSV2003).

The most frequently reported solicited systemic AEs (ie, reported in more than 30% of participants) for adult Ad26 participants were malaise (53.8%), fatigue (48.3%), headache (45.7%), and myalgia (38.3%), all of which were more frequent for Ad26 participants compared with placebo (36.4%, 30.7%, 30.0%, and 17.7% of placebo participants, respectively). Most of these events were considered related to the study vaccine. Pyrexia (9.9%) and vaccine-related pyrexia (9.0%) were also reported more frequently after administration of an Ad26-based vaccine compared with placebo (3.5% and 2.9%, respectively).

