If the neonate/infant has a SARS-CoV-2 positive nasal swab collected on COVID-19 Day 1-3 or from outside the study, then the parent(s)/caregiver(s) will be asked to undertake the COVID-19 procedures with the neonate/infant until 14 days after symptom onset (COVID-19 Day 15, if applicable) or until **resolution of the COVID-19 episode**, whichever comes last^a. Resolution of the COVID-19 episode is defined as having 1 SARS-CoV-2 negative nasal swab and 2 consecutive days with no COVID-19-related signs or symptoms. Once past COVID-19 Day 15, nasal swabs will no longer be collected from the neonate/infant as soon as 1 nasal swab is SARS-CoV-2 negative, but (if the neonate/infant is still symptomatic at that time) the parent(s)/caregiver(s) should continue completing the ObsROs (including PedSIC, body temperature, and pulse oximetry) in the eCOA until 2 consecutive days with no COVID-19-related signs or symptoms.

^a long-term sequelae of COVID-19 will not be followed until their resolution

Note: for neonates/infants who have signs and symptoms present at baseline (assessed pre-vaccination), only signs and symptoms that are associated with COVID-19 and that developed during the COVID-19 episode are to be taken into account.

Upon closure of the COVID-19 episode and procedures, all neonates/infants will fall back to the default Schedule of Activities (Section 1.3.3).

All confirmed COVID-19 episodes will be communicated to the respective parent(s)/caregiver(s) if required per local regulations.

If the neonate/infant experiences new signs or symptoms suggesting possible COVID-19 at a later point in time, the neonate/infant would restart the COVID-19 procedures from COVID-19 Day 1 onwards.

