8.1.2.4. Prespecified Criteria for Suspected COVID-19 in Adults

For adults, the criteria for suspected COVID-19 (ie, the triggers to proceed with contacting the study site and home-collection of the nasal swab) are prespecified as follows:

A positive RT-PCR result for SARS-CoV-2, through a private or public laboratory independent of the study, whether symptomatic or asymptomatic

OR

New onset or worsening of any 1 of these symptoms, which lasts for at least 24 hours, not otherwise explained:

- Headache
- Malaise (appetite loss, generally unwell, fatigue, physical weakness)
- Myalgia (muscle pain)
- Chest congestion
- Cough
- Runny nose
- Shortness of breath or difficulty breathing (resting or on exertion)
- Sore throat
- Wheezing
- Eye irritation or discharge
- Chills
- Fever ($\geq 38.0^{\circ}\text{C}$ or $\geq 100.4^{\circ}\text{F}$)
- Pulse oximetry value $\leq 95\%$, which is a decrease from baseline
- Heart rate ≥ 90 beats/minute at rest, which is an increase from baseline
- Gastrointestinal symptoms (diarrhea, vomiting, nausea, abdominal pain)
- Neurologic symptoms (numbness, difficulty forming or understanding speech)
- Red or bruised looking toes
- Skin rash
- New or changing olfactory or taste disorders
- Symptoms of blood clots: pain/cramping, swelling or redness in your legs/calves
- Confusion
- Bluish lips or face
- Clinical suspicion/judgement by investigator of symptoms suggestive of COVID-19

As several of the prespecified criteria for suspected COVID-19 overlap with vaccine-related reactivity, investigators' clinical judgement is required to exclude vaccine-related events when assessing suspected COVID-19.

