8.1.4. Asymptomatic SARS-COV-2 Infection

An immunologic test for SARS-CoV-2 seroconversion (non-S ELISA and/or SARS-CoV-2 immunoglobulin assay) based on SARS-CoV-2 N-protein, will be performed in adult participants to identify cases of asymptomatic infection.

Asymptomatic infections also include those detected by confirmed molecular tests (either in this study or outside study), in the absence of the relevant symptoms.

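### The adult mild COVID-19 definition in Section 10.8.2 omits the new-or-worsening condition that Sections 10.8.1 and 8.1.2.4 apply, so long-standing symptoms can turn an asymptomatic infection into a mild case

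*Protocol*

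**What the plan says.** Protocol Section 10.8.2 needs two things for mild COVID-19 in an adult: a positive molecular test, and, at some point while the episode is observed, one item from a list that opens "One of the following symptoms: fever" and continues through "malaise (loss of appetite, generally unwell, fatigue, physical weakness), headache, muscle pain (myalgia), gastrointestinal symptoms, cough, chest congestion, runny nose". The one item with a condition attached is "new or changing olfactory or taste disorders".

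Section 10.8.1 (moderate) lists most of the same symptoms and requires two of them, or one from a shorter list of more serious signs. In both lists the sign or symptom must be new or worsening.

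Section 8.1.2.4 (suspected COVID-19 in adults) has two ways in. The symptom arm requires "New onset or worsening of any 1 of these symptoms, which lasts for at least 24 hours, not otherwise explained". The other arm is a positive RT-PCR from a laboratory independent of the study, with no symptom condition.

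Sections 8.1.3 and 9.4.3 send the grading of all cases, and the assessment of asymptomatic and symptomatic infection, to the definitions in 10.8. For the PCR route to the asymptomatic class, Section 8.1.4 has this sentence: "Asymptomatic infections also include those detected by confirmed molecular tests (either in this study or outside study), in the absence of the relevant symptoms".

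**The concern.** Appendix 8 uses two different standards for what counts as a symptom. For moderate disease a complaint that has not changed is ignored; for mild disease the same complaint is sufficient. Fatigue, headache and gastrointestinal complaints can be present in pregnancy without any infection, so the difference is not academic in this population.

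Symptomatic COVID-19 and asymptomatic infection are separate exploratory objectives for adults in Section 3. Within PCR-confirmed infections the asymptomatic class is what remains once the symptomatic definitions have been applied, so a loose mild definition takes cases out of it. The error runs one way: some infections that should be reported as asymptomatic are reported as mild disease after vaccination. Section 8.1.4 does not settle the matter, because it relies on the absence of relevant symptoms without saying which symptoms are relevant.

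**Working it through.** There is no stated figure to reproduce and no calculation applies. The check sets the rules side by side and applies them to defined cases.

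**Conditions on a symptom**

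| Section | New or worsening required? |
|---|---|
| 8.1.2.4, symptom arm | Yes, with a minimum duration and no other explanation |
| 8.1.2.4, outside RT-PCR arm | No symptom needed |
| 10.8.1, moderate | Yes, for both lists |
| 10.8.2, mild | No, except taste and smell |

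**Case A.** A positive outside RT-PCR; fatigue present since before vaccination and unchanged; nothing else. She enters through the outside RT-PCR arm of 8.1.2.4. Under 10.8.1 the fatigue does not count. Under 10.8.2 fatigue is an element of malaise, so she is mild.

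**Case B.** As A, with an equally long-standing headache. These are two different symptoms on the moderate list, but neither is new or worsening, so she is not moderate. Under 10.8.2 either one makes her mild. The same two complaints are disregarded by one definition and sufficient for the other.

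**Case C.** New cough, entry through the symptom arm, then a positive swab. She has already met a stricter test than 10.8.2 and is mild on any reading. No error.

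**Case D.** Infection found only by N-protein serology. Section 10.8.2 requires a molecular test, so it cannot reclassify her. No error.

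The gap therefore concerns Cases A and B. No routine swab is scheduled after Day 1 (Sections 1.3.1 and 1.3.2), so the main way to be PCR-positive without having met the symptom arm is an outside test.

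**Do the earlier steps close the gap?** Partly. After a positive outside test, Section 8.1.2.1 has the woman complete the surveillance check first, and the SIC only if she has COVID-19-like complaints. Section 4.1 describes that check as asking about new symptoms or health concerns. A woman with nothing new may therefore never open the SIC. Once she does open it, the SIC asks what was present in the past 24 hours, not what has changed, and 10.8.2 counts whatever is recorded. The SIC completed before vaccination (footnote p of both adult schedules) would show what was already there, but 10.8.2 does not refer to it.

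**The case against.** The strongest reply is that the affected group is narrow and already filtered. Symptom-arm entrants have passed a stricter test, outside-test entrants first answer a question about new symptoms, serology-only infections are untouched, and a footnote ties the observation period to the COVID-19 episode rather than to the whole pregnancy. All of this stands, and it limits the reach of the point. It does not remove the mismatch, because the filter decides who completes a questionnaire, not which answers count.

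It could also be said that handling of baseline symptoms belongs in the SAP. A derivation rule may well sit there, but the protocol itself states the case definition, and states it differently for two adjacent severity grades.

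A reader might infer more than the documents support in four respects.

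- **A percentage.** Section 2.3.1 gives solicited symptom rates after Ad26-based vaccines (malaise 53.8% in adults, for example). These are pooled from other Ad26 vaccines and not from pregnant women, and they bear on infections that happen to fall in the few days after dosing. Section 2 reports 50 of 62 infected women admitted for obstetric reasons as asymptomatic, but that is an external hospital cohort. No background rate of pregnancy symptoms is given. None of these measures the error in this trial.
- **Vaccine reactions.** One could ask for the 24-hour and no-other-explanation conditions of 8.1.2.4 to be added to the mild and moderate definitions. Section 8.1.2.4 does say that "clinical judgement is required to exclude vaccine-related events when assessing suspected COVID-19", but at the suspicion stage. After PCR confirmation in an open-label trial, the same rule could attribute true COVID-19 symptoms to the vaccine and understate disease. That is a trade-off, not a correction.
- **The moderate list.** It already requires new or worsening signs, so no error is shown there.
- **The infant note.** Under the neonate and infant procedures the protocol says that "only signs and symptoms that are associated with COVID-19 and that developed during the COVID-19 episode are to be taken into account". It stands with the rules for closing an episode, not with case classification, so it is weak evidence of a rule left out for adults.

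**Conclusion.** The mismatch is real and minor. Section 10.8.2 lacks a condition that 10.8.1 places on largely the same symptoms, and the literal result is that unchanged, long-standing complaints make a PCR-positive woman a mild case.

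The consequence is limited to the exploratory, descriptive split between asymptomatic and symptomatic infection in adults. It moves cases only from asymptomatic to mild; the total of PCR-confirmed infections and the moderate and severe classes do not change, and no primary or secondary endpoint is affected. Its size cannot be derived from the document, which gives neither the expected number of outside positive tests nor the frequency of long-standing symptoms among these women.

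The conclusion assumes that 10.8.2 is applied as written and that no derivation rule elsewhere restores the missing condition.

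**What to change.** In Section 10.8.2, change the opening of the symptom condition to: *One of the following new or worsening symptoms (relative to the pre-vaccination SIC or status before the episode)*. The second reference is needed because an infection may occur long after the pre-vaccination questionnaire was completed. In Section 8.1.4, add that PCR-positive women who meet neither 10.8.1 nor 10.8.2 are classed as asymptomatic; this also settles which symptoms are relevant.

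The cost is wording. The pre-vaccination SIC is already collected and the COVID-19 episode is already described by interview, so no visit, sample or procedure is added. Some judgement will be needed on whether a complaint has worsened, as 10.8.1 already requires for moderate disease.

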10.8.3. Adult US FDA Harmonized Case Definition for COVID-19

If a participant presents with symptoms as those listed by the US FDA harmonized case definition ([CDC 2020c](#)), the investigator (or designated medically trained clinician) should assess if these are suggestive of COVID-19:

- A SARS-CoV-2 positive RT-PCR or molecular test result from any available respiratory tract sample (eg, nasal swab sample, sputum sample, throat swab sample, saliva sample) or other sample; AND
- COVID-19 symptoms consistent with those defined by the US FDA harmonized case definition ([CDC 2020c](#)) at the time of finalization of this protocol: fever or chills, cough, shortness of breath or difficulty breathing, fatigue, muscle or body aches, headache, new loss of taste or smell, sore throat, congestion or runny nose, nausea or vomiting, diarrhea.

10.8.4. Neonates and Infants Case Definition for Moderate to Severe/Critical COVID-19

Case Definition for Moderate COVID-19

- A SARS-CoV-2 positive RT-PCR or molecular test result from any available respiratory tract sample (eg, nasal swab sample, sputum sample, throat swab sample, saliva sample) or other sample.

AND at any time during the course of observation^a:

Any 1 of the following new or worsening signs or symptoms:

- Abnormal respiratory rate^b
 - but still ≤ 70 breaths/minute for neonates and infants < 6 months of age
 - but still ≤ 60 breaths/minute for infants ≥ 6 months of age
- Abnormal saturation of oxygen (SpO₂) but still $> 90\%$ on room air at sea level*
- Clinical or radiologic evidence of pneumonia
- Intercostal retractions (in-drawing)
- Heart rate ≥ 160 beats/minute for neonates (≤ 28 days of age) and ≥ 140 beats/minute for infants > 28 days to ≤ 12 months of age)
- Rash
- Bloodshot eyes

Any 2 of the following new or worsening signs or symptoms:

- Fever ($\geq 38.0^{\circ}\text{C}$ or $\geq 100.4^{\circ}\text{F}$)
- Shaking chills or rigors
- Wheezing
- Cough
- Malaise as evidenced by 1 or more of the following^{**}:
 - Poor feeding
 - Moodiness (frequent crying, irritability)
 - Lethargy/tiredness
- Gastrointestinal symptoms^{**} (diarrhea, vomiting)
- Red or bruised looking feet or toes

OR

* SpO₂ criteria will be adjusted according to altitude.

** Having 2 or more elements of a symptom (eg, vomiting and diarrhea or lethargy and loss of appetite/poor feeding) is counted only as 1 symptom for the case definition. To meet the case definition, a participant would need to have at least 2 different symptoms.

^a Participants will be asked to undertake the COVID-19 procedures until 14 days after symptom onset (COVID-19 Day 15) or until **resolution of the COVID-19 episode**, whichever comes last (see Section 8.1.2).

^b Per Golan-Tripto I et al 2018.

Case Definition for Severe/Critical COVID-19

- A SARS-CoV-2 positive RT-PCR or molecular test result from any available respiratory tract sample (eg, nasal swab sample, sputum sample, throat swab sample, saliva sample) or other sample

AND any 1 of the following at any time during the course of observation^a:

- Clinical signs at rest indicative of severe systemic illness (respiratory rate ≥ 71 breaths/minute for neonates and infants < 6 months of age and ≥ 61 breaths/minute for infants ≥ 6 months of age^b, heart rate ≥ 180 beats/minute^c, SpO₂ $\leq 89\%$ on room air at sea level*, or PaO₂/FiO₂ < 300 mm Hg)

*SpO₂ criteria will be adjusted according to altitude

- Respiratory failure (defined as needing high-flow oxygen, non-invasive ventilation, mechanical ventilation, or ECMO)
- Evidence of shock (defined as systolic blood pressure < 65 mmHg to 75 mmHg for neonates and < 100 mm Hg for infants, or requiring vasopressors)
- Significant acute renal, hepatic, or neurologic dysfunction
- Multisystem inflammatory syndrome (MIS-C)^d
 - symptoms: fever, vomiting, diarrhea, rash, bloodshot eyes, feeling extra tired
 - trouble breathing, inability to stay awake, bluish lips or face
- Admission to the Pediatric ICU
- Death

^a Participants will be asked to undertake the COVID-19 procedures until 14 days after symptom onset (COVID-19 Day 15) or until **resolution of the COVID-19 episode**, whichever comes last (see Section 8.1.2).

^b Per Golan-Tripto I et al 2018.

^c Per Goldstein B et al. 2005

^d Multisystem Inflammatory Syndrome in Children (MIS-C) associated with COVID-19 per CDC website: <https://www.cdc.gov/coronavirus/2019-ncov/daily-life-coping/children/mis-c.html>. Accessed on 12 Nov 2020. Note: the list of symptoms was adapted for neonates and infants.

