8.1.2.5. Prespecified Criteria for Suspected COVID-19 for Neonates

For neonates, the criteria for suspected COVID-19 (ie, the triggers to proceed with contacting the study site and collection of the nasal swab by the HCP) are prespecified as follows:

A positive RT-PCR result for SARS-CoV-2 for the neonate, through a private or public laboratory independent of the study, whether symptomatic or asymptomatic

OR

A positive RT-PCR result for SARS-CoV-2 for a parent/caregiver, or any other close relative of the neonate, through a private or public laboratory independent of the study, whether symptomatic or asymptomatic

OR

New onset or worsening of any 1 of these symptoms^a, which lasts for at least 24 hours, not otherwise explained:

- Fever ($\geq 38.0^{\circ}\text{C}$ or $\geq 100.4^{\circ}\text{F}$)
- Lethargy (decreased activity)
- Nasal congestion or runny nose (rhinorrhea)
- Cough
- Tachypnea (according to age)
- Difficulty breathing
- Vomiting
- Diarrhea
- Poor feeding
- Bluish lips or face
- Bloodshot eyes
- Red or bruised looking feet or toes
- Clinical suspicion/judgement by investigator of symptoms suggestive of COVID-19, including MIS-C

^a Adapted from Section [10.10.2](#)

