8.2.2. Vital Signs

Body temperature (oral route preferred for adults, in accordance with the local standard of care for neonates/infants), pulse/heart rate, respiratory rate, blood pressure (adults only), and blood oxygen saturation will be assessed.

Adult participants will utilize a reactogenicity diary to record body temperature measurements from the time of vaccination until 7 days after vaccination in the eCOA (see Section 8).

All participants with COVID-19 signs and symptoms should measure body temperature daily (in accordance with the local standard of care) and record the highest temperature in the last 24 hours each day in the ePRO in the eCOA, for the duration of follow-up of COVID-19 episodes (as defined in Section 8.1.2.1).

All parent(s)/caregiver(s) of neonates/infants with (suspected) COVID-19 should measure blood oxygen saturation 3 times a day and body temperature daily (the highest temperature in the last 24 hours each day) and record it in the eCOA for the duration of follow-up of COVID-19 episodes (as defined in Section 8.1.2.2).

Blood pressure and pulse/heart rate measurements should be preceded by at least 5 minutes of rest in a quiet setting without distractions (eg, television, cell phones). Vital signs are recommended before blood sampling.

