10.8.5. Neonates Case Definition for Mild COVID-19

- A SARS-CoV-2 positive RT-PCR or molecular test result from any available respiratory tract sample (eg, nasal swab sample, sputum sample, throat swab sample, saliva sample) or other sample;

AND at any time during the course of observation^a:

- One of the following symptoms: fever ($\geq 38.0^{\circ}\text{C}$ or $\geq 100.4^{\circ}\text{F}$), poor feeding, tachycardia, lethargy, diarrhea, vomiting, cough, or rhinorrhea.

A case is considered clinically mild when it meets the above case definition but not the moderate to severe/critical definition in Section 10.8.4.

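### The neonate and infant COVID-19 severity classes leave SpO2 of 90% and isolated difficulty breathing unplaced, and give the neonatal blood pressure limit as a range

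*Protocol*

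**What the plan says.** Section 8.1.3 has the severity of every COVID-19 case graded by the definitions in Section 10.8. Section 9.4.3 applies them to neonates and infants among the exploratory analyses.

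- **Oxygen saturation, Section 10.8.4.** The moderate class accepts "Abnormal saturation of oxygen" as long as it stays above 90% on room air at sea level. The severe/critical class opens with "Clinical signs at rest indicative of severe systemic illness (respiratory rate", and its saturation limit is 89% or lower.
- **Breathing signs.** "Difficulty breathing" is a stand-alone trigger for suspected COVID-19 in neonates (Section 8.1.2.5), and Section 8.1.2.6 has the equivalent for infants. The neonatal mild list in Section 10.8.5 is fever plus "poor feeding, tachycardia, lethargy, diarrhea, vomiting, cough, or rhinorrhea". The infant mild list in Section 10.8.6 is longer but also omits difficulty breathing.
- **Shock, Section 10.8.4.** The severe class includes "Evidence of shock (defined as systolic blood pressure" below 65 to 75 mmHg in neonates or below 100 mm Hg in infants, or a need for vasopressors.
- **Blood pressure collection, Section 8.2.2.** The vital signs list reads "blood pressure (adults only"). The infant schedules (Sections 1.3.3 and 1.3.5) and the infant COVID-19 visits in Section 8.1.2.2 list temperature, heart rate and respiratory rate, without blood pressure.

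**The concern.** A severity scale used for tabulation should put every confirmed symptomatic case in exactly one class, and a worse value should never give a milder grade. Here the saturation limits leave a hole between moderate and severe, one respiratory trigger symptom has no class of its own, and one blood pressure limit is not a single number. These rules are fixed in the protocol itself, so they are not details left for the SAP. At stake is the severity split of confirmed COVID-19 in neonates and infants. Enrollment has ceased, so that split may rest on few cases and one ungraded or misgraded infant would show.

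**Working it through.** The plan gives no figure to reproduce. The check runs the rules as written.

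**1. Saturation limits side by side (room air, sea level)**

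| Scale | Moderate | Severe | Whole-number gap |
|---|---|---|---|
| Adult SpO2 (10.8.1) | above 93% | 93% or lower | none |
| Neonate/infant SpO2 (10.8.4) | above 90% | 89% or lower | **90%** |
| Respiratory rate, under 6 months (10.8.4) | 70 or lower | 71 or higher | none |
| Respiratory rate, 6 months and older (10.8.4) | 60 or lower | 61 or higher | none |

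Only the neonate/infant saturation pair fails to meet. Strictly, the hole runs from just above 89% up to and including 90%. Take a PCR-positive infant whose only other sign is cough, and suppose 91% counts as abnormal:

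- 91%: moderate, through saturation.
- 90%: no saturation criterion is met, so the infant is mild through cough.
- 89%: severe.

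The order moderate, mild, severe is not monotone. With no other listed sign, 90% gives no class at all.

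**2. Difficulty breathing as the only sign**

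- Section 10.8.4, moderate on one sign: abnormal respiratory rate, abnormal saturation, pneumonia, intercostal retractions, raised heart rate, rash, bloodshot eyes. Not listed.
- Section 10.8.4, moderate on two signs: fever, shaking chills or rigors, wheezing, cough, malaise, gastrointestinal symptoms, red or bruised feet or toes. Not listed.
- Sections 10.8.5 and 10.8.6, mild: not listed.
- Section 10.8.4, severe: trouble breathing appears only beneath the MIS-C item.

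A PCR-positive neonate or infant with this sign alone is therefore ungraded unless MIS-C is diagnosed. In adults the same symptom alone is moderate (Section 10.8.1).

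**3. Neonatal systolic limit**

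Read at its lower end, the criterion is met below 65 mmHg; read at its upper end, below 75 mmHg. Values under 65 qualify on either reading and values of 75 or more on neither. Whole-number readings from 65 to 74 mmHg cannot be assigned. Study visits do not schedule the measurement in infants, so any value would have to come from elsewhere.

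**4. How much could this matter?**

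The protocol gives neither the number of infant cases nor how often one presents only in a gap, so both are assumed. With m cases and a probability q per case,

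P(at least one affected) = 1 − (1 − q)^m

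| m | q = 1% | q = 5% | q = 10% |
|---|---|---|---|
| 2 | 0.02 | 0.10 | 0.19 |
| 5 | 0.05 | 0.23 | 0.41 |
| 10 | 0.10 | 0.40 | 0.65 |
| 20 | 0.18 | 0.64 | 0.88 |

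For example, 1 − 0.95^10 = 0.40. If one case is misgraded, the split moves by 1/10 = 10 percentage points with 10 cases, or 1/5 = 20 points with 5.

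**The case against.** The strongest defence is that the definitions apply at any time during observation. Section 8.1.2.2 asks for home oximetry three times a day in infants with signs or symptoms. Staff also measure saturation at Day 4-7 and Day 29, and procedures last at least 14 days or until resolution. Any other abnormal reading above 90% makes the infant moderate, and any reading of 89% or lower makes it severe. An error needs 90% to be the only abnormal value and no other sign that places the infant correctly. Likewise, an infant struggling to breathe will often show an abnormal respiratory rate, a low saturation or retractions, each sufficient for moderate. All of this stands: it makes affected cases less likely but does not close the gaps.

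Four stronger readings are tempting, and the documents do not support them.

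- *Severity counts will be wrong.* This would require a case to fall in a gap, which is possible but not certain.
- *The shock criterion cannot be applied.* The vasopressor limb works. The infant limb is a single value and can be used if a hospital record supplies a blood pressure. Section 8.2.2 describes the study's own vital signs and does not bar other records. Only the neonatal blood pressure limb is undefined.
- *The infant limit of 100 mm Hg contradicts the adult limit of 90.* These are different populations, and calling it an error would need clinical norms from outside the documents.
- *Every trigger symptom must have a severity class.* Bluish lips or face, and red or bruised feet or toes, also have no infant class on their own. But the triggers are a broad screen for swabbing, and the protocol never says the lists must match. The adult lists do not match either: confusion triggers a swab but is in neither the mild nor the moderate list.

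Nor does the infant severity endpoint in Section 3 rest on these rules. It is measured by the PedSIC.

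**Conclusion.** The point holds as a drafting defect of small, exploratory consequence. The neonate and infant classes are neither exhaustive nor single-valued in three places: saturation of 90%, isolated difficulty breathing, and neonatal systolic pressure of 65 to 74 mmHg. Severity grades under Section 10.8 may therefore be incomplete or misclassified. Over the assumed ranges (2 to 20 cases, 1% to 10% presenting only in a gap), the chance that any case is affected runs from 0.02 to 0.88. That width reflects how little the protocol says about either input. The number of molecularly confirmed infant cases, PedSIC severity and all primary and secondary endpoints are unaffected. The reversal of order around 90% follows from the text alone, provided 91% counts as abnormal.

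**What to change.** Reconcile Sections 8.1.2.5, 8.1.2.6, 8.2.2 and 10.8.4 to 10.8.6 on three items:

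- Make the moderate and severe saturation limits contiguous, so that every abnormal reading falls in exactly one class.
- Put isolated difficulty breathing in neonates and infants into a stated class.
- Replace the neonatal systolic range with one cut-off or explicit age bands, and say where the value comes from (hospital records, since the study does not schedule it).

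The clinical team sets all values and the class, before infant cases are graded. The cost is a few lines of wording in Appendix 8, with no new visits, measurements or data.
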